**Table 2: Schedule of Assessments**

Study Period	Screening Period m	Titration Period		Maintenance Period a		ET b
Study/Period Day	-28 to -1	Once a week for 2 to 8 weeks as applicable c	72 hr ( $\pm 1$ day) Post Initial Dose and Up-Titration Visit d	Maintenance Day 1, Day 8, Day 15, Day 22	End of Maintenance Visit Day 29 m	ET 14 ( $\pm 2$ ) days after last dose of XP-8121
Informed consent	X					
Inclusion/exclusion criteria	X					
Medical history and concomitant medication review	X					
Complete physical examination e	X				X	X
Abbreviated physical examination e		X	X			
Height	X					
Weight	X				X	X
BMI	X					
12-lead ECG f	X		X		X	X
Vital signs g	X	X	X		X	X
Serology (HCV, HBsAg, & HIV)	X					
Clinical safety laboratory tests h	X			X	X	X
Free and total T4 i	X	X	X	X	X	X
TSH	X	X	X	X	X	X
Urine drug screen k	X					
Urine pregnancy test l	X	X		X	X	X
XP-8121 administration n		X		X j		
PK blood sample collection for substudy subjects only o				X	X	
Modified Draize Scale p		X		X		
Injection Site Discomfort Evaluations q		X		X		
Subject Preference Survey					X r	X r
TSQM-9 s		X		X		
Monitoring of AEs & non-study medications t	X	X	X	X	X	X

Abbreviations: AE = adverse event; BMI = body mass index; BP = blood pressure; CRU = Clinical Research Unit; ECG = electrocardiogram; eCRF = electronic case report form; ET = Early Termination; fT4 = free thyroxine; HBsAg = hepatitis B surface antigen; HCV = hepatitis C virus; HIV = human immunodeficiency virus; PK = pharmacokinetic; SC = subcutaneous; T4=Thyroxine; TSH = thyroid-stimulating hormone; TSQM-9 = Treatment Satisfaction Questionnaire for Medication - 9 items

- a: Dose changes will only be allowed as outlined in Section 7.4.3 during the Maintenance Period.
- b: **Early Termination:** Subjects who withdraw prematurely from the study will be encouraged to return to the CRU for an ET Visit 14 ( $\pm 2$ ) days after their last dose of XP-8121.
- c: Subjects will return to the clinic weekly (every 7 days) for assessments (including administration of XP-8121). XP-8121 will be titrated biweekly as needed. Once subjects have completed the Titration Period, they will continue at the same dose of XP-8121 in the Maintenance Period for 4 weeks (Section 7.4.2)
- d: Following the initial dose and any up-titration, subjects will be required to return for an outpatient visit 72 hr [ $\pm 1$  day] after the up-titration has occurred for the following assessments: ECG, vital signs, abbreviated physical examination, T4 and TSH collections and monitoring of AEs and non-study medications.
- e: See Section 12.8.2 for details on complete and abbreviated physical examinations.

Protocol XP-8121-120

XP-8121 (levothyroxine sodium) injection

- f: **12-lead ECG** to be assessed prior to vital signs and blood draws. ECGs will be taken after remaining in the supine position for at least 10 minutes. Note that at Screening only, the order of ECGs, vital signs, and blood draw procedures are allowed to vary. All potentially clinically significant automated ECG readings should be repeated within 5 minutes of the reading. If potentially clinically significant reading is confirmed, then the ECG will be sent to a local cardiologist for review (Section 12.8.5). See Section 11.5 for further details on procedure order. [Table 3](#) outlines windows for assessment timepoints.
- g: **Vital signs:** triplicate measurements of systolic and diastolic BP and heart rate/pulse will be taken at intervals of 1 to 2 minutes after being in a supine position for at least 10 minutes. Respiratory rate and oral body temperature will also be measured. When the time of scheduled vital sign measurements coincide with a blood draw, vital sign measurements are to be performed before the blood draw where possible, ensuring the blood draw is within the window specified in the protocol. See Section 11.5 for further details on procedure order. [Table 3](#) outlines windows for assessment timepoints.
- h: **Clinical Safety Laboratory evaluation** (hematology, chemistry, and urinalysis): Clinical safety laboratory testing will be performed at Screening, the beginning and the end of the Maintenance Period, and the ET Visit, if needed. Subjects are required to fast from all food and drink except water for  $\geq 10$  hr prior to collection when glucose values will be obtained. Fasting will not be required for the other safety laboratory testing, and when a safety recheck is deemed necessary and the glucose value is not included. See Section 11.5 for further details on procedure order.
- i: Each subject's qualification fT4 level must be within the normal range (study reference range: 0.78 to 1.42 ng/dL) at Screening. During the Titration Period, subjects will come into the clinic once a week for 2 up to 8 weeks, as applicable, for dosing administration. Based on fT4 levels, XP-8121 will be titrated biweekly by intervals of 25% of the target dose. See Section 7.4.2 for further details on dose titration and adjustment criteria during the Titration Period. [Table 3](#) outlines windows for assessment timepoints.
- j: Once subjects have completed the Titration Period, they will continue at the same dose of XP-8121 in the Maintenance Period for 4 weeks unless the conditions described in Section 7.4.3 are met.
- k: **Urine drug screen:** Repeat urine drug screens are permitted for suspected false positive results. If results of the drug screen are positive for a prescribed benzodiazepine, then the subject is eligible to participate in the study. See Section 12.8.8 for description of urine drug screen.
- l: A urine pregnancy test is required during the Screening Period to confirm eligibility for women of childbearing potential only. A urine pregnancy test also will be performed every 2 weeks (ie, Weeks 1, 3, 5 and 7) during the Titration Period, at Day 1 (Week 1) of the Maintenance Period, at the End of Maintenance Visit and, if applicable, at the ET Visit. If the urine pregnancy test results are positive, a serum pregnancy test will be performed for confirmation.
- m: **Oral levothyroxine administration:** Subjects must be receiving a stable dose of oral levothyroxine (Synthroid or an FDA-approved generic equivalent to Synthroid) or, if in the PK substudy, Synthroid for at least 3 months prior to Screening to be eligible for trial. During Screening subjects will continue their prescribed daily dose of oral levothyroxine. After all other procedures at the End of Maintenance Visit, subjects will restart their previously prescribed daily oral levothyroxine, at the dose they were taking before the study.
- n: **XP-8121 administration:** The XP-8121 SC initiation dose will correspond to 50% of the target XP-8121 dose, which is calculated as the current daily oral levothyroxine dose multiplied by 4, rounded up to the nearest 50  $\mu$ g. Based on fT4 levels XP-8121 will be titrated biweekly by intervals of 25% of the target dose. See Section 7.4.2 and Section 7.4.3 for further details about dose titration and dose adjustment criteria during the Titration and Maintenance Periods, respectively. The time of weekly (every 7 days) XP-8121 SC dose administration will remain consistent throughout the study and will occur within  $\pm 2$  hours of the time of the XP-8121 SC initiation dose (Section 10.5).
- o: A subgroup of subjects (~12), who have been on Synthroid for at least 3 months prior to Screening and who have maintained adequate trough T4 (free and total) levels in the Maintenance Period will participate in a PK substudy. The study reference ranges for T4 (free and total) and TSH are: 0.78 to 1.42 ng/dL (fT4), 5.53 to 10.96  $\mu$ g/dL (total T4), and 0.47 to 4.68  $\mu$ IU/mL (TSH). During Week 4 of the Maintenance Period, subjects will be housed in the CRU for 9 days and 8 nights to undergo PK sample collections at specified timepoints as outlined in [Table 5](#). Subjects will be admitted to the CRU on Maintenance Day 21 (day prior to XP-8121 administration and initiation of PK sampling) and discharged from the CRU on Maintenance Day 29 (168 hr PK sample).
- p: **Modified Draize Scale:** Injection site erythema and edema will be assessed using Modified Draize Scales 30 ( $\pm 5$ ) minutes after injection of XP-8121. If the Draize score is  $>1$  at 30 minutes, the subject will be discharged, and a follow up visit will be scheduled at 24 ( $\pm 3$ ) hr post-dose to allow the Investigator or designee to complete an assessment of the injection site using the Modified Draize Scale.
- q: **Injection Site Discomfort evaluations:** Injection site discomfort will be assessed at 10 ( $\pm 2$ ) minutes after injection of XP-8121 using the Numeric Rating Scale for Injection Discomfort, and subjects will complete a Site Discomfort Description and Duration Questionnaire 10 ( $\pm 2$ ) minutes after injection.
- r: **Subject Preference Survey:** Survey will be completed during the End of Maintenance Visit or Early Termination Visit.

Protocol XP-8121-120

XP-8121 (levothyroxine sodium) injection

---

- s: **TSQM-9:** During first visit of the Titration Period prior to dosing, subjects will be asked to complete the questionnaire regarding their oral levothyroxine use. Subjects will also complete on Maintenance Day 22 after the last administration of XP-8121.
- t: All **AEs and non-study medications** must be recorded on the subjects' eCRF from the time of consent and followed until resolution or maximally up to 14 days after the End of Maintenance. Medications used prior to the time of informed consent will be recorded as prior medications.

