### 8.4. Subject Withdrawal Criteria

Subjects may withdraw their consent to participate in the study at any time. If a subject withdraws consent, the date and reason for consent withdrawal should be documented. Wherever possible, the tests and evaluations described for the Early Termination Visit in Section 11.4 should be performed for all subjects who discontinue prior to the completion of the study. Subject data, including the results of sample testing, will be included in the analysis up to the date of the withdrawal of consent. The reason for withdrawal must be specified on the appropriate electronic case report form (eCRF), including further specification if the category of 'Other' is selected.

Individual subjects will be advised verbally and in the written informed consent form (ICF) that they have the right to withdraw from the study at any time. The Investigator or sponsor may discontinue a subject from the study in the event of an intercurrent illness, adverse event, death,

positive pregnancy test at any time during the study, other reasons concerning the health or well-being of the subject, or in the case of lack of cooperation, non-compliance, protocol deviations, or other administrative reasons. In addition, potential reasons for early termination from the study include:

- Inability to achieve an adequate replacement dosage
- Inability to achieve a tolerable replacement dosage

If a subject is withdrawn from the study, a replacement subject will not be enrolled (Section [7.2.1](#)).

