### 11.3. Maintenance Period

Once subjects have completed the Titration Period, they will continue at the same dose of XP-8121 in the Maintenance Period for 4 weeks. All subjects will return to the CRU weekly for dosing before having an End of Maintenance Visit.

The following procedures will be conducted once a week for 4 weeks (Day 1, Day 8, Day 15, and Day 22), as applicable, unless specified differently below:

- Clinical safety laboratory testing (hematology, chemistry, and urinalysis) on Day 1 (Week 1 Maintenance Period). See Section [12.8.7](#) for details. See Section [8.6.2.2](#) for fasting requirements.
- Free and total T4 and TSH measurements every week
- Urine pregnancy test (WOCBP only) on Day 1 (Week 1 Maintenance Period) (See Section [12.8.9](#) for details)
- XP-8121 administration (See Section [10.5](#))
- Modified Draize Scale to be completed 30 ( $\pm 5$ ) minutes after each XP-8121 injection. If the Draize score is  $>1$  at 30 minutes, the subject will be discharged, and a follow up visit will be scheduled at 24 ( $\pm 3$ ) hr post-dose to allow the Investigator or designee to complete an assessment of the injection site using the Modified Draize Scale. See [Appendix E](#) for details.
- Injection Site Discomfort Evaluations to be completed (see [Appendix C](#)): Numeric Rating Scale for Injection Site Discomfort to be done 10 ( $\pm 2$ ) minutes after injection as well as Injection Site Discomfort Description and Duration Questionnaire completed 10 ( $\pm 2$ ) minutes after each XP-8121 injection.
- TSQM-9 questionnaire to be completed on Maintenance Day 22 after last administration of XP-8121.
- Review of AEs and changes in concomitant medication

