#### 13.5.3.1. Analysis of Exploratory Endpoints

All exploratory endpoints except for PK endpoints will be analyzed for the safety population, for subjects with primary hypothyroidism only and for all subjects, if applicable. TSH, total and free T4 measures and changes from baseline will be summarized by each protocol-specified timepoint using descriptive statistics. Analysis of PK endpoints will be described in Section 13.6.

The analysis of the exploratory endpoint of TSQM-9 domain scores will be gated on results from the primary endpoint analysis. The three domain scores will be hierarchically analyzed to ensure control of the family-wise type I error rate at the 0.05 level, with the Convenience score first, Overall Satisfaction score second, and Effectiveness third. Hypothesis tests for the three domain scores will be based on null hypotheses that assume no difference between oral levothyroxine and once-weekly XP-8121 SC treatments. Each domain score will be compared between the two treatments using a paired t-test.

Subject counts and percentages for each answer to each question from the Subject Preference Survey will also be presented.

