## **13.9. Statistical Issues**

### **13.9.1. Missing or Imputed Data**

No statistical adjustments for missing data will be conducted.

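### TSQM-9 on XP-8121 is taken only at Maintenance Day 22, so a comparison labelled Safety Population uses only subjects who reach that dose and may favour the injection

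*Protocol*

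**What the plan says.** **Collection.** The oral score comes first (Protocol Table 2, footnote s): "During first visit of the Titration Period prior to dosing, subjects will be asked to complete the questionnaire regarding their oral levothyroxine use". The XP-8121 score has one time point, given in the same footnote: "Subjects will also complete on Maintenance Day 22 after the last administration of XP-8121". Section 11.3 repeats it: "TSQM-9 questionnaire to be completed on Maintenance Day 22 after last administration of XP-8121". The TSQM-9 row of Table 2 has no mark in the Early Termination (ET) column, and the ET procedures in Section 11.4 do not include it. The Subject Preference Survey is collected there (Table 2, footnote r): "Survey will be completed during the End of Maintenance Visit or Early Termination Visit".

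**Analysis.** Protocol 13.5.3.1: "All exploratory endpoints except for PK endpoints will be analyzed for the safety population". SAP Section 7 also assigns the non-PK exploratory endpoints to the Safety Population, meaning everyone with at least one dose, and SAP 6.8 and 9.7 restrict them to primary hypothyroidism. The test is stated in Protocol 13.5.3.1: "Each domain score will be compared between the two treatments using a paired t-test". The three domains are tested in a fixed order under a family-wise 0.05 claim. The protocol gates this testing on the primary analysis.

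**Missing data.** Protocol 13.9.1: "No statistical adjustments for missing data will be conducted". SAP 8.3 says that missing data points are in general not replaced. The TSQM-9 rules in SAP 6.8 deal with missing items within a form, not with a missing form. Withdrawn subjects are not replaced (Protocol 7.2.1).

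**Reasons for stopping.** Protocol 8.4 lists adverse events, failure to reach an adequate dosage, and "Inability to achieve a tolerable replacement dosage". It also lists reasons that need have nothing to do with satisfaction, such as pregnancy and administrative reasons.

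**The concern.** A paired test needs both scores from the same subject. With one XP-8121 time point at the last Maintenance dose, the set analysed is the subjects who reached that dose, not the Safety Population that the plan names. SAP 9.7 speaks of tests at each time point, but no second XP-8121 time point exists. It gives TSQM-9 no sensitivity analysis, although it repeats the T4, fT4 and TSH summaries in the Completer Population.

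The subjects left out are not likely to be a random sample of those treated. Someone who stops because the injection is poorly tolerated or does not provide adequate replacement would probably score it low, and that score is never collected. A positive satisfaction result could then partly reflect who remained. TSQM-9 has its own sample-size calculation and a formal testing order, so its p-values are likely to be read as more than descriptive.

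**Working it through.** **Inputs from the documents.** SD of differences 20, target difference 10, two-sided alpha 0.05, power 80%, 34 subjects, 44 enrolled (Protocol 13.1, SAP 4.4).

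**Inputs assumed.** The number missing (m) and the gap (g) between completers and stoppers in mean score difference, XP-8121 minus oral. The documents give neither.

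**Step 1: reproduce the plan's figure.** The normal approximation gives n = (20 × (1.960 + 0.842) / 10)² = 31.4, rounded up to 32. With the noncentral t distribution, power is 0.795 at n = 33 and 0.808 at n = 34. The stated 34 is confirmed. At the same inputs, 38 pairs give 0.851 and 44 pairs give 0.900, so the issue is bias and not power.

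**Step 2: size of the bias.** Let c be the mean difference in completers and s that in stoppers, with g = c − s. The mean over all treated subjects is ((44 − m)c + m·s) / 44 = c − (m/44)g. The test estimates c, so it overstates the all-treated mean by (m/44) × g. This takes all 44 as treated and eligible for the analysis.

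| Missing of 44 | g = 10 | g = 20 | g = 30 |
|---|---|---|---|
| 2 | 0.45 | 0.91 | 1.36 |
| 4 | 0.91 | 1.82 | 2.73 |
| 6 | 1.36 | 2.73 | 4.09 |

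Against the target difference of 10, this is about 5% to 41%. With g = 0 or m = 0 the bias is zero.

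**Step 3: effect on a single domain test.** Suppose the all-treated difference is truly 0 and the SD is 20. The chance of a significant result favouring the injection, nominally 2.5%, follows from the noncentral t with 44 − m pairs and mean (m/44)g:

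| Missing of 44 | g = 10 | g = 20 | g = 30 |
|---|---|---|---|
| 2 | 3.5% | 4.7% | 6.3% |
| 4 | 4.7% | 8.1% | 13.2% |
| 6 | 6.1% | 12.7% | 23.2% |

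**Step 4: would filling missing differences with zero be enough?** Take 38 pairs with mean 10 and SD 20, so t = 10 / (20/√38) = 3.08. Add six zeros:

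- mean = 380/44 = 8.64
- sum of squares about the mean = 37 × 400 + 38 × 100 − 44 × 8.636² ≈ 15,318
- SD = √(15,318/43) = 18.9
- t = 8.64 / (18.9/√44) = 3.04

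The estimate falls by 1.4 points, but the test statistic hardly moves because the constant fill also shrinks the SD. The sensitivity analysis therefore needs values below zero and a method that keeps the variance honest.

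**The case against.** **Direction is not shown.** A reader might infer that the result will be tilted towards XP-8121. The documents do not establish that. They contain no scores for stoppers, and several listed stopping reasons are neutral. This objection stands: the tilt is a reasoned expectation.

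**Six of 44 is not a dropout allowance for TSQM-9.** A reader might take 44 − 38 = 6 as the plan's expected loss. But 38 is the sample size for the dose conversion factor, and the margin up to 44 also covers subjects whose TSH is not normalized. Those who stay to Day 22 still give a score, and no split is stated. This also stands, so the 2 to 6 used here is an assumption. With 3 missing, the range for a gap of 10 to 30 would be 0.7 to 2.0 points.

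**Not every early leaver is lost.** Someone who leaves after the Day 22 dose counts. Subjects with a lowered dose, or who enter Maintenance without adequate fT4, can also reach Day 22. This is correct, and it limits the number missing.

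**The loss is visible.** The missing-data rule is stated, SAP 9.7 reports n for each domain, discontinuations are tabulated with reasons, and the Preference Survey partly captures stoppers' views. This helps a reader see that scores are missing. It does not show how the TSQM-9 difference would change.

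**ET scores measure something different.** The ET Visit falls 14 (±2) days after the last dose, and the subject may have had only a partial titration dose. That is a fair reason to keep ET scores out of the main test and confine them to a sensitivity analysis.

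**Stakes are low.** The endpoint is exploratory and, under the protocol, gated on the primary analysis. That lowers the priority. The gate adds no scores from stoppers, so it does not affect the bias.

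**Conclusion.** The point holds as a cheap improvement. The set tested is the subjects who reach the Day 22 dose, while the plan names the Safety Population, and nothing in either document closes that gap for TSQM-9. The estimate may be biased towards XP-8121 by (m/44) × g. That is about 0.5 to 4.1 points for 2 to 6 of 44 missing and a gap of 10 to 30 points, all of which are assumptions, and zero if nobody stops or stoppers do not differ.

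A reader might also conclude that the TSQM-9 sample size is wrong. It is not: 34 reproduces, and power stays at 80% or above at the stated inputs as long as 34 pairs remain. The dose conversion factor analysis is not affected.

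**What to change.** 1. **Collection.** In Protocol Table 2 and Section 11.4, add TSQM-9, asked about XP-8121, to the ET Visit next to the Subject Preference Survey.
2. **Main analysis.** Keep the Day 22 paired t-test. State that it uses subjects with both scores, and report the number of pairs against the Safety Population with primary hypothyroidism, as the SAP restricts it.
3. **Sensitivity analysis in SAP 9.7.** Use the ET score where Day 22 is missing. For subjects with neither score, apply a range of unfavourable mean differences, for example 0, −10 and −20, by a method that does not artificially shrink the variance, such as delta-adjusted multiple imputation.

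**Cost.** Nine items at an existing visit for a few subjects, and one extra analysis. The drawback is recall about 14 days after the last dose, possibly of a partial titration dose. ET attendance is only encouraged, so some scores will still be missing and item 3 is needed in any case. If collection has already finished, items 2 and 3 can still be done without new data, using the assumed differences alone.

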**Table 3: Timing Window Allowances for T4 and TSH, Electrocardiogram, and Vital Sign Measurements**

Timepoint a	Tolerance Window
T4 and TSH Sampling	
Titration Period: Predose	within 10 minutes of dosing
Titration Period: 72 hr	72 hr ( $\pm 1$ day) following initial dose and up titration
Maintenance Period: Predose	within 10 minutes of dosing
Early Termination Visit	14 ( $\pm 2$ ) days following last dose of XP-8121
Electrocardiogram	
Titration Period: 72 hr	72 hr ( $\pm 1$ day) following initial dose and up titration
Early Termination Visit	14 ( $\pm 2$ ) days following last dose of XP-8121
Vital Sign Measurements	
Titration Period: Predose	within 10 minutes of dosing
Titration Period: 72 hr	72 hr ( $\pm 1$ day) following initial dose and up titration
Early Termination Visit	14 ( $\pm 2$ ) days following last dose of XP-8121

Abbreviations: T4 = thyroxine; TSH = thyroid stimulating hormone

a Timepoints are not all inclusive of all required samples needed in study as some visits do not have associated windows

